8.4.3	Risk-Benefit Assessment	13
8.5	RECRUITMENT STRATEGY.....	13
8.5.1	Subjects	13
8.6	INFORMED CONSENT/ASSENT AND HIPAA AUTHORIZATION.....	14
8.6.1	Payments to parent for time and inconvenience (i.e. compensation)	14
8.6.2	Gifts	15
9	PUBLICATION	15
10	REFERENCES	15
	Appendix	17

ABBREVIATIONS AND DEFINITIONS OF TERMS

ROR	Reach Out and Read
LDI	Leonard Davis Institute
AH	Automated Hovering
NICHHD	National Institute of Child Health and Human Development
StimQ	Measure of Cognitive Stimulation Provided in the Home
PSI-SF	The Parenting Stress Index-Short Form
CDI	MacArthur Communicative Development Inventory
DECA	Devereux Early Childhood Assessment

ABSTRACT

Context:

Early childhood is a sensitive period in which young children develop language and socio-emotional skills foundational for school readiness. Unfortunately, poor vulnerable children experience disparities in these critical areas of development. Parent-child shared reading can help ameliorate these disparities, yet low-income parents do not consistently engage in this activity. Behavioral economics approaches utilizing automated hovering (AH) have the potential to increase parent-child shared reading through text messages and financial inducements.

Objectives:

- 1) To assess the feasibility and acceptability of 3 novel AH interventions of increasing complexity hypothesized to increase the frequency of parent-child shared reading.
- 2) Explore relevant outcomes related to parenting stress, the home reading environment, and language and socio-emotional development.

Study Design:

The study design has two phases, Phase 1 and Phase 2. Phase 1 is a brief, rapid cycle design process. Phase 2 is a prospective, randomized comparative group trial to test the effects of AH approaches to increase parent-child shared reading.

Setting/Participants:

We plan to recruit 3-4 urban CHOP-affiliated pediatric practices from CHOP's Pediatric Research Consortium (PeRC) to participate in the study. These practices care for a diverse, complex urban population and have onsite social workers to assist with family crises.

A total of 65 eligible children and their parents will be recruited from participating practices to achieve a diverse sample of children. Ten will participate in Phase 1 and 55 will participate in Phase 2. Inclusion and exclusion criteria for Phase 1 will be the same as Phase 2. Children will be eligible to participate if they are 6-24 months old, and have a parent with daily access to a smart phone in order to receive and send text messages. Children born <35 weeks EGA or with congenital anomalies or genetic syndromes that place them at high risk for developmental disabilities will be excluded.

Study Intervention and Measures:

Ten participants in phase 1 will undergo an audio-recorded qualitative interview that will be used to develop coaching tips for phase 2.

Forty-five participants in phase 2 will be randomized to receive one of the 3 AH interventions: daily text message reminders, daily text message reminders with coaching or daily text message reminders with coaching and weekly lottery entries. The weekly lottery is related to principles of behavioral economics so that participants in this group will be externally motivated. The lottery is testing a methodology and is not a non-permissible form

of payment. There will be 15 participants per group to adequately assess feasibility and acceptability.

The result of this application would be expected to inform future R01 applications on the effects of AH to improve parent-child shared reading in a larger and more diverse population of low-income children.

TABLE 1: SCHEDULE OF STUDY PROCEDURES

Study Phase	Screening/ Study Visit 1 (Baseline)	Intervention Period (8 weeks)	Follow-up Study Visit (8-12 weeks)
Phase 1			
Informed Consent	X		
Review Inclusion/ Exclusion Criteria	X		
Audio-recording of Qualitative Interview	X		
Phase 2			
Informed Consent	X		
Review Inclusion/ Exclusion Criteria	X		
Randomization	X		
8 Weeks of Daily Text Messaging +/- Coaching +/- Weekly Lottery		X	
Demographics	X		
StimQ-Read	X		X
PSI-SF	X		X
CDI			X
DECA			X
Satisfaction Rating			X
Parent Questionnaire			X

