After conducting the rapid-cycle design for phase 1, forty-five eligible children and their parents will be consented and enrolled in the study. In the event that the baseline visit cannot be completed in-person an alternative method of obtaining informed consent electronically through REDCap will be used. Following informed consent and completion of baseline surveys, participants will be stratified by site and randomized 1:1:1 to receive one of the 3 AH interventions for an 8-week duration. Using a similar recruitment strategy, we were able to successfully recruit 120 (81%) of 148 low-income infants and their parents who were approached for the aforementioned study on early literacy promotion.

Group 1 will consist of daily text messages on shared reading, which will be sent to participants using the Way to Health Platform. Participants will be asked to reply to the text message on daily shared reading activities including the titles of books and time spent reading. Group 2 will consist of Group 1 plus personalized coaching. Personalized coaching content will be made available to participants through links in the text messages and will provide comparisons of their reading frequency with that of other participants. These comparisons will be blinded to preserve confidentiality. Finally, Group 3 will consist of Group 2 plus availability of a weekly lottery. Group 3 participants who report back that they read on a particular day will be entered into a weekly drawing to receive \$20. Each reported daily reading behavior will provide a single lottery entry so that participants who report they read all 7 days in a given week will have 7 entries in the weekly drawing.

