3.4 Study Population

We plan to recruit 3-4 urban CHOP-affiliated pediatric practices from CHOP's Pediatric Research Consortium (PeRC) to participate in the study. These practices care for a diverse, complex urban population and have onsite social worker to assist with family crises. Using well-established methods that have proven effective in multiple large-scale trials, 3-4 practices located in Philadelphia will be recruited to participate using letters of invitation and in-person presentations. Incentives to participate will include provider education on parent-child shared reading. A total of 55 eligible children and their parents will be recruited from participating practices to achieve a diverse sample of children. Inclusion and exclusion criteria for Phase 1 will be the same as Phase 2. Children will be eligible to participate if they are 6-24 months old, and have a parent with daily access to a smart phone in order to receive and send text messages.

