6.4.2 Sample Size Justification

The planned sample size for Phase 1 is 10 participants and for Phase 2 is 15 participants per group. Ten participants in phase 1 will be sufficient to provide information to develop coaching tips and identify the main obstacles to parent child reading in phase 2. Our target sample size for phase 2 is 45 participants with 15 participants per group. This sample size is based on the availability of funds and ability to complete the study within a 1 year time period.. These sample sizes were determined to adequately assess feasibility and acceptability. As a pilot study, a power calculation is not necessary.

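### The Abstract's 65 in total and 55 in Phase 2 conflict with the 45 in Phase 2 given later in the Abstract and in Sections 3.1.2 and 6.4.2, and with the total of 55 in Section 3.4

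*Combined protocol and SAP*

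**What the plan says.** The planned size appears in six places.

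- **Abstract, Setting/Participants.** The total is 65: "A total of 65 eligible children and their parents will be recruited from participating practices to achieve a diverse sample of children". The split follows: "Ten will participate in Phase 1 and 55 will participate in Phase 2".
- **Abstract, Study Intervention and Measures.** "Forty-five participants in phase 2 will be randomized to receive one of the 3 AH interventions", and then "There will be 15 participants per group to adequately assess feasibility and acceptability".
- **Section 3.1.2, Phase 2.** After Phase 1, "forty-five eligible children and their parents will be consented and enrolled in the study".
- **Section 3.3.2.** Recruitment ends at about 55 enrolled subjects. The section does not say whether this covers one phase or both.
- **Section 3.4, Study Population.** The Abstract's sentence recurs with a different number: "A total of 55 eligible children and their parents will be recruited from participating practices to achieve a diverse sample of children".
- **Section 6.4.2, Sample Size Justification.** Phase 1 has 10 participants, and "Our target sample size for phase 2 is 45 participants with 15 participants per group". The reason given is practical: "This sample size is based on the availability of funds and ability to complete the study within a 1 year time period". The section says that a pilot needs no power calculation.

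**The concern.** A reader who wants to know how many families Phase 2 will take finds both 45 and 55. For the whole study the answers are 55 and 65. The number 55 therefore appears once as a Phase 2 figure and once as a study total. Section 3.3.2, which governs when recruitment ends, uses 55 without saying which is meant.

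What is at stake is practical. Section 6.4.2 ties the size to funds and a one-year period, so the planned number acts as the resource limit. The feasibility and acceptability results in Section 6.4.3.1 are proportions and counts of participants, and they will be reported against the planned number. The plan should leave no doubt whether Phase 2 recruitment ends at 45 or at 55.

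**Working it through.** **Inputs**

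- Phase 1: 10 (Abstract; Section 6.4.2).
- Phase 2 groups: 3, with 15 per group (Abstract, Study Intervention and Measures; Section 6.4.2).
- Stated Phase 2 sizes: 55 (Abstract, Setting/Participants) and 45 (Abstract, Study Intervention and Measures; Sections 3.1.2 and 6.4.2).
- Stated totals: 65 (Abstract, Setting/Participants) and 55 (Section 3.4).
- Payments: up to $25 in Phase 1; in Phase 2, $25 after baseline and $50 at follow-up, $75 at most (Section 8.6.1).

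**Step 1: the Abstract's own sum.** 10 + 55 = 65. The addition is correct, so the fault is not in the sum.

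**Step 2: the size from the design.** Phase 2 = 3 × 15 = 45. Total = 10 + 45 = 55. This agrees with the Abstract's later paragraph and with Sections 3.1.2, 3.4 and 6.4.2. It does not agree with 65/55. Nor does 55 divide evenly into three groups (55/3 = 18.3).

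**Step 3: size of the gap.** Total: 65 − 55 = 10. Phase 2: 55 − 45 = 10, and 10/45 = 22%.

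**Step 4: can 55 be an enrolment allowance?** For 55 enrolled to leave 45 randomised, the loss before randomisation would be 10/55 = 18.2%. The documents give no such rate.

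**Step 5: the two readings of Section 3.3.2**

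| Reading of the 55 | Phase 1 | Phase 2 | Total |
|---|---|---|---|
| Both phases together | 10 | 45 | 55 |
| Phase 2 only | 10 | 55 | 65 |

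The heading of Section 3.3.2 concerns the total number of subjects, and Section 3.4 gives 55 as a total, so the first row is the more natural. The second row is the Abstract's Setting/Participants figure, and nothing in Section 3.3.2 excludes it.

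**Step 6: participant payments, excluding the lottery**

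- 10 + 45 families, all visits completed: 10 × $25 + 45 × $75 = $250 + $3,375 = $3,625.
- 10 + 55 families, all visits completed: 10 × $25 + 55 × $75 = $250 + $4,125 = $4,375.
- Upper end of the difference: 10 × $75 = $750 (750/3,625 = 21%).
- If the ten extra families complete only baseline: 10 × $25 = $250.
- If they leave before completing baseline: about $0.

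**The case against.** The strongest defence is that 55 and 45 count different things: 55 families enrolled in Phase 2 and 45 randomised. The Abstract speaks of recruiting in one place and randomising in the other. Randomisation comes after the baseline surveys, and Section 4.5 disenrols families who do not complete those surveys within 30 days. Some enrolled families may therefore never be randomised. This reading is possible, but no section states it. Section 3.1.2 applies 45 to enrolment itself ("forty-five eligible children and their parents will be consented and enrolled in the study"), and the total of 55 in Section 3.4 fits it poorly. If it is what was intended, the text still needs correcting. What stands of the defence is that the documents prove a conflict without proving how the 55 arose.

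Three stronger readings are tempting, and the documents do not support them.

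- *The Abstract contradicts the rest of the plan.* Part of it does. Its later paragraph gives 45 and 15 per group, so a team reading the whole Abstract would meet both figures.
- *The stop rule is defective because it counts enrolled rather than randomised families.* Section 3.3.2 gives only an approximate number, and counting enrolled subjects is ordinary wording. A disenrolled family can plainly be read as no longer enrolled. Table 1 places consent, baseline measures and randomisation at the same visit, so little loss between them seems to be expected. A clarifying sentence would help, but this is not an error.
- *The larger number would exceed the funds.* The documents contain no budget, and $750 is only the upper end of the extra payments.

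**Conclusion.** Wrong as written; minor. The Abstract's 65 in total and 55 in Phase 2 cannot stand beside the 45 in Phase 2 given in its own later paragraph and in Sections 3.1.2 and 6.4.2, or beside the total of 55 in Section 3.4. The weight of the text favours 10 + 45 = 55. Because Section 3.3.2 names no phase, the conflict carries into the point at which recruitment ends.

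The difference is 10 families, 22% of 45. In participant payments it is about $0 to $750 excluding the lottery, depending on whether the extra families complete both visits. That range assumes the payments in Section 8.6.1; no rate of loss before randomisation is assumed, because none is given. A reader might infer that the pilot's power or precision is at risk. The plan sets no target for either, so no such figure is affected.

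**What to change.** In the Abstract, Setting/Participants, change the total to 55, with 10 in Phase 1 and 45 in Phase 2. In Sections 3.3.2 and 3.4, write the 55 as 10 + 45. Sections 3.1.2 and 6.4.2 can then stay as they are.

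If 55 was meant as an enrolment allowance for Phase 2, state that in the Abstract and change Sections 3.1.2, 3.3.2 and 3.4 to match: up to 55 enrolled in Phase 2, 45 randomised, and a study total of up to 65.

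As an optional clarification, Section 3.3.2 may add that families disenrolled before randomisation do not count towards the 45.

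The first option costs a wording amendment to three places, with no change to design or analysis. The second also touches Section 3.1.2 and allows recruitment of up to ten more families, at the payment cost shown above.

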1 BACKGROUND INFORMATION AND RATIONALE

Early childhood is a sensitive period in which young children develop foundational skills necessary for communication.¹ Early stimulation of brain centers involved in language processing promotes the development and sustainment of critical neuronal connections leading to growth and proficiency in language and social functioning.¹ Unfortunately, language and socio-emotional delays are common among children under 3 years of age,² particularly for children residing in impoverished communities.³ These delays contribute to poor educational and functional outcomes later in childhood and represent an important cause of disparities in child educational achievement.⁴ Lifetime costs for individuals with resulting disabilities have been estimated to exceed \$60 billion in 2003 U.S. dollars.⁵ The etiology of these delays are multifactorial but have been associated with deficits in early parent-child verbal interactions.^{6,7}

Parent-child shared reading represents an important source of language stimulation that can enhance language and socio-emotional development in young vulnerable children and help mitigate disparities in later educational achievement.⁸ Previous studies have found that parent-child shared reading is associated with improved language functioning, better school performance, less harsh parenting, and fewer disruptive behaviors especially for children from low-income families.⁹⁻¹² Yet parents of young children from low-income communities do not consistently engage in reading activities with their children until they are older, due to numerous barriers such as lack of time, lack of understanding of importance, difficulty developing daily reading habits, stress and fatigue, and competing priorities.¹³ From an economics viewpoint, these barriers can impose a time bias that discounts future language and socio-emotional benefits in favor of the current costs of shared reading.

Early shared reading strategies, such as Reach Out and Read (ROR) and Imagination Library, promote parent-child shared reading and distribute board books to low-income children.^{8,14} These strategies have demonstrated greater interest in shared reading and improved child language development compared to usual care among poor children and their families. However despite these beneficial effects, low-income children and their families engaged in these programs have only shown modest improvements in the frequency of shared reading and still lag behind their higher income peers in language development.¹⁵

1.1 Introduction

The overall goal of this LDI pilot grant proposal is to incorporate behavioral economics approaches using automated hovering (AH) to improve the frequency of early parent-child reading behaviors among low-income families. Such approaches have previously shown benefit in medication adherence, smoking cessation, immunization rates, health care utilization, and weight management and have the potential to shape parent-child reading behaviors and improve language and socio-emotional development in young children.¹⁶⁻²¹ This application addresses the care of vulnerable populations, one of LDI's four priority research areas. If successful, behavioral economics approaches can be incorporated into current early literacy promotion strategies to maximize their potential and further improve early language and socioemotional development. For example, children participating in ROR at participating pediatric practices can be signed up to receive automated text message reminders with or without financial inducements at the same time as they receive a board book and reading promotion counseling from their pediatric clinician at a corresponding well child visit.

1.2 Name and Description of Intervention

The intervention will incorporate behavioral economic approaches utilizing AH to improve frequency of early parent-child shared reading through text messages. The intervention consists of daily text messages for 8 weeks in 3 AH intervention groups. The text messages were part of the aforementioned trial on early literacy promotion (see Appendix 1).

Group 1 of the program will consist of daily text messages on shared reading, which will be sent to participants using the Way to Health Platform. Participants will be asked to reply to the text message on daily shared reading activities including the titles of the books and time spent reading (see Appendix 1).

Group 2 will consist of Group 1 plus personalized coaching. Personalized coaching content will be made available to participants through links in the text messages.

Group 3 will consist of Group 2 personalized coaching plus availability of a weekly lottery. The lottery is related to principles of behavioral economics so that participants in group 3 will be externally motivated. The lottery is testing a methodology and is not a non-permissible form of payment. Participants who report back that they read on a particular day will be entered into a weekly drawing to receive \$20. Each reported daily reading behavior will provide a single lottery entry so that participants who report they read all 7 days in a given week will have 7 entries in the weekly drawing. Lottery entries will begin on Mondays and close at 12:00 AM on Sundays for all 8 weeks of the program. The following Monday morning the lottery will be drawn. The participants in Group 3 will begin their 8- week intervention the first Monday after enrollment.

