3.1.3 Randomized Trial

All participants across groups will be asked to report on daily reading behaviors by replying to daily text messages. In addition, participants will be asked to complete study measures using a RedCap survey at baseline and following the 8-week intervention period. Responses to daily reading text messages will be provided by the Way to Health platform and will be assessed as the mean overall number of days/weeks of reading for each group. Participants will also be provided with an opt out of the daily text messages option if they no longer desire to receive daily text messages. Participants will be queried at follow-up on their overall satisfaction (5-point Likert scale) with their intervention group and asked to answer survey questions regarding likes and dislikes concerning the intervention group they received following the intervention period. The survey questions at the end of phase 2 will be based on input from the rapid-cycle design process of phase 1 interviews.

At baseline, parents will complete a measure of demographics (child and parent age, race/ethnicity, sex, highest education completed, and family income category) (see Appendix 2). To explore differences in the home reading environment, parents will complete the Read subscale of the StimQ, a validated 14-item parent report measure of the home reading environment, at baseline and follow-up.²³ To explore differences in parenting stress, participants will complete the Parenting Stress Index-short form (PSI-SF), a validated 36-item parent report of parenting stress, at baseline and following the 8-week intervention in order to assess changes.²⁴ Finally to explore differences in child language and socio-emotional development, parents will complete at follow-up the MacArthur Communicative Development Inventory (CDI), a validated parent-report scale of early language development, and the Devereux Early

Childhood Assessment (DECA), a validated 33-item parent report of socio-emotional problems.^{25,26}

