6 STATISTICAL CONSIDERATIONS

6.1 Primary Endpoint

For phase 1, the primary endpoint will be the qualitative interview responses used to inform texts and survey for phase 2. For phase 2, the primary endpoints will be acceptability and feasibility of the intervention. To determine feasibility and acceptability of the intervention, we will assess the number of participants who complete the daily text messages and query participants on their overall satisfaction measure (5-point Likert scale) with their intervention group and provide survey questions regarding likes and dislikes concerning the intervention group they received following the intervention period.

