6.3 Control of Bias and Confounding

Randomization and allocation concealment are the primary means of avoiding bias. Analytic strategies will also be used to control for residual confounding: (1) Stratification will control for imbalance not controlled by design. (2) Additional potential confounders will be evaluated for any residual association with treatment and included in model as needed. (3) Post randomization effects: The primary source of bias will arise after randomization from dropout and loss to follow-up. To address this problem and avoid missing data, we shall implement the following measures: (a) incentives to each family to complete the study, (b) collection of multiple contact numbers and tracking of changes, and (c) contact all randomized participants, even if they do not continue with their clinical contacts.

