6.4.3 Analysis of Primary Outcomes of Interest

6.4.3.1 Specific Aim 1

Primary outcomes:

To determine the feasibility of each group of the intervention, we will assess the proportion of participants who receive and report a daily reading behavior each week across all groups, the proportion of participants who access coaching content in group 2 & 3, and the proportion of participants who participate in the weekly lottery in group 3. To determine acceptability of the intervention, we will assess the number of participants who opt out of the daily text messages and query participants on their overall satisfaction (5-point Likert scale) with their intervention group and provide survey questions regarding likes and dislikes concerning the intervention group they received following the intervention period. The survey questions at the end of phase 2 will be based on input from the rapid-cycle design process of phase 1 interviews. Differences in weekly reading frequency and satisfaction scores between groups will be assessed using standard inferential statistics and intention-to-treat analysis. Survey question responses will be assessed using qualitative methods in which codes will be developed and emerging themes identified by consensus of investigators using NVivo software.

Secondary outcomes:

To explore differences in reading frequency, the home reading environment, parenting stress, and child language and socio-emotional development, we will examine differences in mean weekly reading frequency, mean changes in StimQ Read Subscale scores and PSI-SF scores, and mean CDI and DECA scores between groups using standard inferential statistics and intention-to-treat analysis. In addition, effect sizes will be computed to assess differences between Group 1 and each of the other 2 groups and to power future studies.

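### Only Group 3 is rewarded for texting that reading took place, and those texts are the reading-frequency outcome, so a Group 3 difference mixes reading with reporting

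*Combined protocol and SAP*

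**What the plan says.** Parents in all three groups are asked to "reply to the text message on daily shared reading activities including the titles of the books and time spent reading" (section 1.2; section 3.1.3 confirms that every group reports). In Group 3 only, the reply also has a monetary value: "Participants who report back that they read on a particular day will be entered into a weekly drawing" for $20. Each reported day is one entry, up to seven a week. Section 3.1.2 repeats this for Group 3, and section 8.6.1 puts the maximum at $160 (8 x $20).

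The replies are also the outcome. Section 3.1.3: "Responses to daily reading text messages will be provided by the Way to Health platform and will be assessed as the mean overall number" of days read in each group. Section 8.1.2 says parents know their assignment. Section 6.4.3.1 states, under primary outcomes, "Differences in weekly reading frequency and satisfaction scores between groups will be assessed using standard inferential statistics and intention-to-treat analysis". It lists weekly reading frequency again among the secondary outcomes and adds that "effect sizes will be computed to assess differences between Group 1 and each of the other 2 groups and to power future studies".

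Reporting itself is measured, but as feasibility: "we will assess the number of participants who complete the daily text messages" (section 6.1) and "the proportion of participants who receive and report a daily reading behavior each week across all groups" (section 6.4.3.1). On bias arising after allocation, section 6.3 says "The primary source of bias will arise after randomization from dropout and loss to follow-up", and the measures it lists concern retention. Section 6.4.3.1 gives no rule for a day without a reply.

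**The concern.** The measuring instrument is rewarded in one arm and not in the other two. A higher count in Group 3 can arise in three ways: families read more, families reply on more of the days they read, or families report reading that did not happen. The second needs no dishonesty. A Group 1 parent who reads but does not reply may simply be counted as not having read.

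Randomisation does not remove this, because the difference in measurement begins after allocation. Analysis by intention to treat does not remove it either. The likely direction favours Group 3. At stake is the reading-frequency conclusion for Group 3 against Group 1 or Group 2, and the effect size that would be carried into a later trial.

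**Working it through.** **Tracing the link.** The lottery entry depends on the report (1.2, 3.1.2). The report is the datum (3.1.3). The datum is tested and converted to an effect size (6.4.3.1). The supplied text describes no verification. Book titles and reading time are requested, but they are self-reported too.

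**Illustration.** The plan states no figure to reproduce. From the documents: 15 per arm and 8 weeks of daily texts (56 days). Assumed: equal true reading in both arms, with family probability p of reading on a day having mean 0.5 (3.5 days a week) and SD s/7, with s = 2 days a week (range 1.5 to 2.5); all reply and false-report rates.

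Reported days are binomial(56, q).
- Weekly mean = 7E(q)
- Weekly variance = [56 E(q(1-q)) + 56² Var(q)]/64
- d = difference in means / pooled SD

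At s = 2, Var(p) = (2/7)² = 0.0816 and E(p²) = 0.25 + 0.0816 = 0.3316.

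*(a) Honest replies, 80% of days answered against 60%; unanswered counted as no reading.*
- Group 3, q = 0.8p: mean 7 x 0.40 = 2.80; variance [56 x 0.1878 + 3136 x 0.0522]/64 = 2.72; SD 1.65.
- Group 1, q = 0.6p: mean 7 x 0.30 = 2.10; variance [56 x 0.1806 + 3136 x 0.0294]/64 = 1.60; SD 1.26.
- Pooled SD 1.47; d = 0.70/1.47 = 0.48 (0.61 at s = 1.5; 0.39 at s = 2.5).
- With 70% or 90% against 60%, d = 0.26 or 0.66.
- Simulated Welch tests at 15 per arm give p < 0.05 in about 23% of trials (36% at s = 1.5; 16-17% at s = 2.5), against about 5% expected without bias.

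*(b) Same honest replies, answered days only (simulation).* If the extra replies are spread evenly over all days, d = 0. If they fall only on reading days, 3.84 against 3.50 days, d = 0.17 (0.10 to 0.26 over the SD range).

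*(c) Every day answered; Group 3 reports reading on some non-reading days.*
- 10%: q = 0.1 + 0.9p; 3.85 against 3.50; d = 0.18.
- 20%: q = 0.2 + 0.8p; 4.20 against 3.50; d = 0.38.
- Range over both rates and all SDs: 0.15 to 0.49. Both unanswered-day rules give the same answer, so comparing them cannot reveal over-reporting.

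*(d) Non-reading days draw no reply.* The answered-days value is 7 of 7 in every arm, and only the first rule is usable.

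**Sensitivity.** Case (a) gives every family in an arm the same reply rate. If reply rates have mean m and SD t between families, independent of reading, then Var(q) = (m² + t²)E(p²) - (0.5m)². At t = 0.20 the SDs are 1.83 and 1.50, d = 0.42. At t = 0.30 they are 2.04 and 1.74, d = 0.37.

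**Precision.** The 95% half-width of d at 15 per arm is 1.96 x sqrt(2/15 + 0.48²/60) = 0.73, or 0.72 at d = 0.

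**The case against.** The strongest reply is that this is a pilot. Feasibility and acceptability are the primary aim, reading frequency is exploratory (2.2, 6.2), and section 6.4.2 makes no power claim. The frequency comparison under primary outcomes can be read as a comparison of reported behaviour, where a lottery effect on replying is a proper finding. Effect sizes cover every secondary outcome, and an estimate with a half-width of about 0.7 is a poor planning input with or without this bias. All of that limits the consequence. It does not remove it: informing later trials is a stated purpose, and bias adds to imprecision.

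The illustration can also be faulted for giving every family in an arm one reply rate. That stands; allowing variation lowers d from 0.48 to between 0.37 and 0.42. The inputs are assumed throughout, so this trims an example and leaves the mechanism intact.

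Requiring titles and time may discourage false reports, but does nothing about unequal replying. Appendix 1, which holds the message format, was not supplied, so the absence of a check can be asserted only of the text available.

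Two further points are fair. Groups 2 and 3 also see comparisons with other participants' reading (3.1.2, 3.2), which might influence reporting, and Group 3 against Group 1 includes coaching. The lottery mechanism does not touch Group 2 against Group 1, but that contrast is not thereby shown to be clean. StimQ-Read is weak corroboration: 15 per arm has 80% power only for d of about (1.96 + 0.84) x sqrt(2/15) = 1.02, so a null result there would say little.

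**Conclusion.** The concern holds. As written, the plan can report a Group 3 gain in reading frequency, and supply an effect size for planning, that is partly or wholly a gain in reporting. The mechanism follows directly from the text. The size cannot be derived from it: under the assumptions above, the spurious d runs from 0 to about 0.7, depending on reply rates, false reporting, family variation and the rule for unanswered days. That rule is unstated and largely decides how much of unequal replying enters the contrast. Feasibility and acceptability conclusions stand. This should be fixed before analysis, because choosing the rule after seeing the data would allow a selective result.

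**What to change.** Amend section 6.4.3.1 as follows.

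1. Call the text-based count reported reading. State that a Group 3 contrast on it will not by itself be interpreted as more reading or used to size a future trial.
2. Beside the reporting measure already planned, show the reply rate by arm and, if replies saying no reading took place are captured, the share of answered days with reading. Give the between-group contrast twice: unanswered days counted as no reading, and answered days only. State that the pair addresses unequal replying and cannot detect over-reporting. If such replies are not captured, say so and give only the first version, with that limitation.
3. Name the planned StimQ-Read change as the corroborating measure for Group 3 contrasts, since payment is not tied to it. Note that it is unblinded parent report of the home reading environment, not a count of days, and that at this sample size a null result is uninformative.

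The cost is analysis wording and one table, with no change to the intervention. The answered-days column depends on a reply option that the supplied text does not confirm. The Group 3 conclusion becomes more cautious, and the trial will still lack a count of days read that is free of the incentive.
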